- ② Secondary objectives: To explore the improvement of cardioembolic stroke, cardiovascular complex events, recurrent stroke and all-cause death risk, quality of life, and cardiac function in the "multidisciplinary assisted diagnosis and treatment mode" group and the "routine diagnosis and treatment model group". The conventional diagnosis and treatment mode can match the patients not adopted in the same period and "multidisciplinary assistance in diagnosis and treatment mode".

Design type: A non-intervention, prospective, observational, real-world study (at least 1.5 years). No fixed diagnosis and treatment plan is set up in advance, and only a multidisciplinary assisted diagnosis and treatment mode is established. All treatment options are completely made by the clinicians who follow the expert consensus of relevant textbooks and clinical guidelines, and they are formulated according to the patients' conditions.

Study subjects: Collect high-risk patients from the Second Affiliated Hospital of Nanchang University and various hospitals of Jiangxi Province from September 2022 to September 2023.

Selection criteria: ① met the high embolic risk (including intracardiac thrombosis, intracardiac tumor, aortic atherosclerosis, atrial fibrillation, and spontaneous development of ultrasound) in the risk stratification criteria of The Chinese Expert Consensus on Cardiac stroke Diagnosis (2020); ② meets the surgical indications for cardiac diseases related to the Chinese Expert Consensus on the Treatment of Cardioembolic Stroke (2022) (including left atrial fibrillation occlusion, left atrial fibrillation ligation, and radiofrequency ablation of atrial fibrillation recommended for high-risk stroke patients with atrial fibrillation; Transcatheter PFO occlusion is recommended for cryptogenic stroke patients with high-risk PFO; Valvular repair or replacement, etc.); ③ understood and voluntarily signed the informed consent form.

Exclusion criteria: ① with severe mental disorder and unable to express intention; ② with other abnormal signs, laboratory tests and clinical diseases, not suitable to attend investigator; ③ and unable to complete long-term follow-up.

Project objectives and assessment indicators: (a) establish a multidisciplinary cooperative diagnosis and treatment mode of cardiovascular and brain joint treatment, and routinely carry out interdisciplinary diagnosis and treatment of cardiovascular and cerebrovascular diseases; (b) develop an optimized diagnosis and treatment process, reduce treatment links, and save medical resources and costs.

Diagnosis and Treatment process (Figure 1):

Primary prevention (mainly for patients with high embolic risk, including valvular heart disease/intracardial tumor, thrombosis/atrial fibrillation/infective endocarditis/PFO, with or without a history of stroke):

- a) Patients with high risk of embolism, such as valvular heart disease/intracardiac tumors, thrombosis/atrial fibrillation/infective endocarditis/PFO, and patients with or without a history of stroke, were screened for stroke risk assessment in primary hospitals.
- b) Imaging diagnosis and treatment, such as cardiac color ultrasound, cardiac CTA, foaming test (right cardiography), transesophageal ultrasound, right atrial angiography, etc., should be developed according to the research needs, and the specialized diagnosis and treatment process at the recommended level should be formulated
- c) Health education and follow-up

Secondary prevention (emergency department mainly for patients with new stroke) :

- a) Primary doctors should do a good job in pre-hospital treatment of suspected stroke patients and transfer the patients to superior hospitals as soon as possible, so as to quickly identify the nature of stroke; Once it is clear that it is ischemic stroke, emergency treatment should be carried out according to the diagnosis and treatment process of ischemic stroke.
- b) When patients with sudden neurological deficits enter the emergency room, the stroke identification procedure and the treatment process of the stroke center should be initiated immediately, mainly using the BEFAST test /FAST test/" stroke 1-2-0 "method;
- c) After the disease stabilized, the examination related to etiological diagnosis should be improved (screening for valvular heart disease/intracardiac tumor, thrombosis/atrial fibrillation/infective endocarditis/PFO);
- d) Health education norms and follow-up

Multidisciplinary assisted care model group: Patients who agreed to and accepted the recommendation of multidisciplinary assisted care mode were enrolled in the multidisciplinary assisted care model group. These patients would undergo further stroke (primary/secondary) prevention intervention, as detailed in the MDT flow chart;

Any of the following treatments (including but not limited to), as recommended by the standard medical procedure, shall be deemed to have received the standard medical treatment; otherwise, they were not.

- 1) Surgical procedures: left atrial appendage ligation, left atrial appendage clip, valve repair or replacement, etc.
- 2) Medical procedures: atrial fibrillation radiofrequency ablation, valvular closure, left atrial appendage closure, PFO closure, etc.
- 3) Anticoagulant drug therapy: standardized anticoagulant drug therapy.

Routine treatment model group: Patients who did not agree to enter the multidisciplinary treatment mode were automatically entered into the routine treatment mode group.

Study end points:

Primary end point: Composite end point of cardiovascular and cerebrovascular events (nonfatal ischemic stroke, Nonfatal hemorrhagic stroke, Nonfatal myocardial infarction, Nonfatal heart failure, and cardiovascular and cerebrovascular death)

Secondary end points: cardiovascular and cerebrovascular death; All-cause death; Cardiac insufficiency; Cognitive dysfunction

[figure not shown]

Figure 1 Flowchart of the project

3. Research background data

1. Project approval basis

Stroke, as the first cause of death in China, has the "three high" characteristics of high morbidity, high disability rate and high mortality rate. Data show that in the next 20 years, the number of stroke patients in China will increase by nearly four times, and the prevention and treatment of stroke has a long way to go. In the subtyping of ischemic stroke, the proportion of cardiac stroke is approximately 14 – 30%^{1, 2}. cardioembolic stroke (CES), hereinafter referred to as cardioembolic stroke, refers to the clinical syndrome of emboli from the heart and aortic arch through the circulation leading to cerebral artery embolism causing the corresponding cerebral dysfunction. The mechanism of cardioembolic stroke is usually summarized into three types: slow blood flow (especially cardiac cavity enlargement, atrial loss of contraction function, left ventricular wall tumor, etc.) thrombosis and shedding; abnormal valve surface attachments (degenerative valve surface calcification, infectious endocarditis, artificial valve surface thrombus, etc.); systemic circulation venous system thrombosis through abnormal ventricular channel (atrial septal defect or closed orifice) causing embolism (namely "contradictory embolism"). CES has more related cardiac diseases or risk factors, among which about 70% are caused by atrial fibrillation (atrial fibrillation, AF). In recent years, the prevention and treatment of CES (such as stroke high-risk AF) has improved¹. However, there are still some problems, such as insufficient understanding and large differences in treatment strategies. Compared with stroke from other causes, the cardiac stroke course is rapidly progressive, with more extensive involvement, associated with more severe complications, and a higher incidence of adverse outcomes³. How to effectively prevent cardioembolic stroke and improve patient prognosis is a major dilemma in clinical practice.

The formulation and effective implementation of accurate treatment plan to improve the prognosis of cardioembolic stroke patients and stroke recurrence is an important means to prevent the onset of patients. Compared with other causes of stroke, the cause of cardiac stroke is clear and mostly preventable and treatable (e. g., an observational study of elderly patients with heart disease history (with AF history) assessing the risk of postoperative thromboembolic complications of LAA occlusion combined with cardiac surgery. The results showed significant reductions in uncorrected thromboembolism readmission rates (4.2% versus 6.2%), all-cause mortality (17.3% versus 23.9%), and the composite endpoint (20.5% versus 28.7%) when compared with those without LAA occlusion⁴. The same study in Asians showed that for high-risk PFO (atrial septal aneurysm, ASA), high activity, primary and secondary spacing 2 mm], PFO occlusion significantly reduced

the main endpoint (stroke, vascular death, thrombolysis defined primary hemorrhage) and stroke recurrence (n=120)⁵. But currently for the prevention and control of cardiac stroke heart brain barriers, diagnosis and treatment process specification, related surgical instruments clinical application is still in the primary stage, such as severe problems, precision treatment need to optimize the current diagnosis and treatment process and professional technology, and an urgent need to "brain", this project plans to explore the above scientific problems, in order to guide the clinical prevention and treatment of cardiac stroke. To explore the multidisciplinary cooperative diagnosis and treatment mode of cardioembolic stroke, and to explore the prevention and treatment mode of "screening, prevention, diagnosis and treatment" of provincial, municipal and county hospitals with the help of medical association and network. This study combined with existing consensus guidelines to develop treatment options based on CES risk stratification and specific pathogenesis^{6,7}. Corresponding therapeutic measures are taken to address the different causes of CES to prevent the occurrence of stroke and to actively conduct neurorehabilitation treatment. Many cardioembolic strokes occur every year in China, and most of the cardiology department treat patients with atrial fibrillation without stroke. Many patients with high-risk CES usually improve anticoagulation and other symptomatic treatment in the neurology department, but have no further systematic investigation of whether it is "cardiac". Many neurologists do not routinely consider cardiac treatment in patients with cardioembolic stroke. Therefore, there is an urgent need for "heart and brain joint governance". For patients with previous stroke, the risk of recurrent stroke is very high if the cause of cardiac thrombosis is not addressed. There are problems in the domestic diagnosis and treatment mode, and the heart, surgery, surgery and nerve surgery are not effectively integrated. In the past two years, relevant domestic societies have issued the guidelines for the prevention and treatment of cardiac stroke (2019) and the Chinese expert consensus on the diagnosis of cardiac stroke (2020)^{8,9}. According to the clinical and imaging characteristics of cardioembolic stroke, apply the preliminary assessment and risk assessment process of cardioembolic stroke (Figure 1): improve cerebral cerebrovascular imaging; 12-lead ECG and dynamic electrocardiogram; transthoracic echocardiography; laboratory examination and other related examinations, and find possible abnormalities. For example: After admission to the neurology department, the patient is routinely screened for atrial fibrillation by completing a general ECG and an ambulatory ECG. If atrial fibrillation is present, there is a high risk of cardioembolic stroke and referral to the cardiology department is required. Further investigation by the cardiology department confirms the presence of thrombus in the atria, and treatment plans are developed and evaluated accordingly. The risk factors are addressed through standardized

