Selection criteria: ① met the high embolic risk (including Valvular heart disease/intracardiac neoplasms, thrombosis/atrial fibrillation/infective endocarditis/PFO) in the risk stratification criteria of The Chinese Expert Consensus on Cardiac stroke Diagnosis (2020); ② meets the surgical indications for cardiac diseases related to the Chinese Expert Consensus on the Treatment of Cardioembolic Stroke (2022) (including left atrial appendicular occlusion, left atrial appendicular ligation, and atrial fibrillation radiofrequency ablation recommended for high-risk stroke patients with atrial fibrillation; Transcatheter PFO occlusion is recommended for cryptogenic stroke patients with high-risk PFO; Valve repair or replacement is recommended for patients with valvular disease. Left atrial appendage ligation or left atrial appendage clip is recommended for patients with atrial fibrillation.); ③ understood and voluntarily signed the informed consent form.

Exclusion criteria: ① with severe mental disorder and unable to express intention; ② with other abnormal signs, laboratory tests and clinical diseases, not suitable to attend investigator; ③ and unable to complete long-term follow-up.

2. Study and design flow chart:

[figure not shown]

Figure 1 Flowchart of the project

3. Sample size determination method required for the study:

This study through the real world cohort research, to cross professional association as a breakthrough point, with standardization, standardization for innovation, establish interdisciplinary diagnosis and treatment team, establish "screening-prevention-diagnosis and treatment" standardized process, for cardiac stroke high-risk patients to choose standard diagnosis and treatment basis, optimize the current diagnosis and treatment process and professional technology. It is expected that 1,200 patients at high risk of cardioembolic stroke will be included in a time period of 1-1.5 years. It should be pointed out that if compared with conventional diagnosis and treatment methods, patients matched with multiple factors in the same period are selected as the control group.

6. Safety evaluation (including the definition and evaluation of adverse events and serious adverse events)

1. Definition of adverse events: adverse medical events that occur in the course of this standard treatment of the subject, whether they are drug-related or not.
2. Abnormal laboratory and instrument examination results.

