3. Serious adverse events: Major adverse events may be drug-related, including but not limited to the following:
 - (a) Abnormal laboratory indicators (including liver and kidney function, etc.);
 - (b) Allergic reaction to antiplatelet drugs / anticoagulants;
 - (c) Stroke / transient ischemic attack or neurological deficit;
 - (d) Spontaneous bleeding: such as petechia, ecchymosis, digestive system and urinary system bleeding;
 - (e) Central nervous system damage.
4. Assessment of the severity level
Light: do not affect the daily activities;
In: affect daily activities;
Heavy: loss of daily activity ability.

7. Data collection and management

1. Survey content (CRF table)

variable:

- a) Basic information of patients: name, gender, age, education level, combined diseases, past medical history, etc.;
- b) Admission status: chief complaints of symptoms, general condition, vital signs, CHA2DS2-VASc score, nutrition questionnaire and epidemiological data etc.;
- c) Pre-treatment laboratory and instrument examination: biochemical indicators, nutrient index (one carbon unit substance), electrocardiogram, dynamic electrocardiogram, cardiac color doppler ultrasound, foaming test, cardiac CTA, craniocerebral CT and MRI, internal and external intracranial artery evaluation, etc.;
- d) Treatment medication; surgical conditions
- e) The occurrence of adverse events during the hospitalization period;
- f) Situation at follow-up: chief complaint of symptoms, general condition, vital signs, Quality of Life, HAS-BLED score, etc.;
- g) Laboratory and instrumental examination at follow-up: biochemical indicators, electrocardiogram, cardiac color ultrasound, cardiac CTA, craniocerebral CT and MRI, internal and external intracranial artery evaluation, etc.;
- h) occurrence of adverse events during follow-up.

2. Data management and statistical analysis

For All the subjects who have signed the informed consent form and are qualified to be selected, all the items in the electronic medical record report form should be carefully recorded in detail, without no empty or missing items.

The investigator records the data into the electronic medical record report according to the original records and inpatient records, and the investigator ensures that the data is true and accurate.

Data that are significantly high or outside the clinical acceptance range should be verified with necessary explanation by the investigator.

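### Minor: in a study declared non-interventional, the only stated basis for imaging that includes transesophageal ultrasound and right atrial angiography is research need

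*Protocol*

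**What the plan says.** Section 2 (Summary), under Design type, describes the study as "A non-intervention, prospective, observational, real-world study (at least 1.5 years". It adds: "No fixed diagnosis and treatment plan is set up in advance". On who decides, it says: "All treatment options are completely made by the clinicians who follow the expert consensus of relevant textbooks and clinical guidelines".

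Further on in Section 2, the diagnosis and treatment process has a primary-prevention branch. Item a is stroke-risk screening at primary hospitals. Item b lists cardiac ultrasound, cardiac CTA, the foaming test and two further examinations, and says of the list: "transesophageal ultrasound, right atrial angiography, etc., should be developed according to the research needs". The sentence then continues: "and the specialized diagnosis and treatment process at the recommended level should be formulated".

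The secondary-prevention branch has a parallel line on examinations, item c: "After the disease stabilized, the examination related to etiological diagnosis should be improved".

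**The concern.** In a non-interventional study, the patient's clinical need determines which tests are done, and the study records the results. Item b puts it the other way round: research need is the reason given for the imaging. For a routine cardiac ultrasound this would hardly matter. But the list includes transesophageal ultrasound, which needs an oesophageal probe, and right atrial angiography, which is catheter-based, and it is left open-ended.

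What is at stake is participant protection and consistency with the declared design. A site that applied item b as written could treat research need as sufficient reason for one of these tests in a patient with no clinical indication for it.

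**Working it through.** No arithmetic applies: the protocol gives no figure on this point. The check is to read item b against every visible place that could restrict it.

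1. **Design type (Section 2).** The statement that nothing is fixed in advance covers diagnosis as well as treatment, so nothing here calls for protocol-driven imaging. The sentence that leaves decisions to clinicians is about treatment options and does not mention diagnostic tests. It therefore does not expressly govern item b.

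2. **Item b itself.** The first half gives research need as the basis. The second half says that a process should be formulated and refers to a recommended level. This may be an allusion to guideline grading, but it qualifies the process and not the reason for imaging a patient.

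3. **Neighbouring items.** The primary-prevention heading names people at high embolic risk, and item a is risk screening. Both give clinical context. Neither states an indication for the two tests. Secondary-prevention item c ties its examinations to finding the cause of the stroke, so the protocol does state a clinical purpose where it means one.

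4. **Background (Section 3).** The worked example is clinically triggered: atrial fibrillation is found, the patient is referred to cardiology, further investigation follows, and a treatment plan is made. It names neither test and sets no limit on them.

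5. **Eligibility (Sections 2 and 5).** Entrants must already meet indications for a cardiac procedure, so many would have such imaging clinically anyway. This narrows the group exposed to the literal reading without removing it.

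6. **Data collection (Section 7, CRF items c and g; Section 8, methods of determination).** Neither test is named. The two CRF lists are open-ended, so this is not conclusive, but it weighs against an intention to collect these tests as research data.

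7. **Safety and risk (Sections 6 and 9).** The possible risks in Section 9 name no examination. Section 6 is broader. It lists "Abnormal laboratory and instrument examination results", and its serious-event list is open: "Major adverse events may be drug-related, including but not limited to the following". CRF items e and h also collect adverse events generally.

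Result: both tests appear only in item b, the only basis given there is research need, and nothing visible restricts them to clinical indication. The surrounding text leans towards a clinical intention without stating it.

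**The case against.** The best defence is that item b is about building a service. Its subject is imaging diagnosis and treatment as an activity, its verb is to develop, and it ends with a process to be formulated. That matches the project's stated aims of setting up a multidisciplinary care mode and an optimised pathway. The wording also reads like a translation and may have meant as clinically needed. The background example and the CRF lists both fit this reading. In addition, Figure 1 is not shown and the consent pages were removed, so indications or examination risks may be set out there.

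Most of this stands, and it is why the point is minor. It does not remove the point: the pathway clause is joined to the imaging clause and gives no indication for imaging. If clinical need was meant, one phrase would say so.

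A reader might infer more than the documents support:

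- *That invasive imaging is required of participants, so the study is in fact interventional.* Item b orders no test for any patient, and the design statement rules out a preset diagnostic plan.
- *That complications of these tests would go unrecorded.* The breadth of Section 6 and of the CRF makes it likely that they would be recorded.
- *That the Section 9 risk list is deficient as it stands.* It would need an examination risk only if a test were kept as a research procedure. How many of its entries could or could not cover an examination harm is no measure of the size of the problem.

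**Conclusion.** The concern holds as a minor inconsistency of wording. The declared design is non-interventional, but item b rests imaging that includes one semi-invasive and one invasive test on research need alone. Read literally, that permits such a test without clinical indication.

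No patient number can be given, because the protocol does not say how many entrants would lack an indication for either test. No consequence for the endpoints, the comparison of the two care models or the analysis is shown or claimed.

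The conclusion assumes that the English text is what sites follow and that the figure and consent form, which are not visible, do not already restrict these tests. If either assumption fails, the point reduces to tidying the sentence.

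**What to change.** In Section 2, primary-prevention item b, replace the reference to research needs with: *according to clinical indication, as decided by the treating clinician*. The clause about formulating a process can stay.

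Only if the sponsor really does want one of these tests for research should it be declared a study procedure, with its risks added to Section 9.

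The cost is one phrase. Loss of data should be negligible, since neither the CRF examination lists nor the methods of determination name either test.

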The researcher will modify the data due to filling reasons, and the dialog box will pop up in the electronic medical record report form, and the researcher should indicate the reason for the modification. Any modification by the researcher leaves a mark to ensure the authenticity of the data.

After the investigator fills in the data and the supervisor monitors, the investigator solves all the data questions and ensures that the accuracy of the data is determined, the data administrator locks the database. The data management personnel, principal researchers, statistical analysts, implementers and monitoring management personnel will jointly review the data, and complete the final definition and judgment of the analysis population, and then the data manager will finally lock the database.

The locked database or files should generally not be changed again.

8. Quality Management Plan (please introduce relevant measures to ensure project quality and progress)

Surveillance of the observational cohort studies

During the study, the inspectors will regularly visit the research center to ensure that all the content of the research protocol is strictly followed, and the original data is checked to ensure that the data filling content is true, complete and correct.

1. Method of determination

(1) Brain CT and MRI;

(2) Electrocardiogram or dynamic electrocardiogram: 12-lead routine electrocardiogram; 24-hour dynamic electrocardiogram monitoring

(3) Blood routine test, urine routine test, liver and kidney function test, blood biochemical indexes: automatic biochemical analyzer;

(4) Nutrients (one carbon unit substance) : mass spectrometry or biochemistry

(5) Cardiac ultrasonography;

(6) Cardiac CTA

(7) Surgical records

(8) Combined medication

(9) Relevant scales should be applied with international common scale or Chinese version

(10) Record of adverse events.

2. Fill in the electronic case report form

Electronic case report form (CRF) was used in this trial. For All subjects who have signed the informed consent form and are qualified to be selected, all items in the electronic medical record report form should be recorded carefully and detail, with no empty or missing items. All data in the EHR report form should be checked with the original subject medical record data to ensure correct accuracy. The investigators ensure that the data are true and accurate.

3. Preservation of the original materials

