Prior to inclusion in this study, the investigator must provide the subject and his relatives with the details of the clinical trial, including the purpose of the trial, expected efficacy, possible adverse events, and countermeasures. They will be selected after the subjects fully understood the trial, accepted the informed process, and signed the informed consent.

The Informed consent was jointly signed by the study physician and the subject himself or his legal representative in duplicate, with one copy kept for each party.

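### Do the MDT and routine group definitions leave patients unassigned, or the start of follow-up undefined?

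*Protocol*

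**What the plan says.** Section 2 (Summary of the research plan) forms the groups by the patient's response to the MDT offer. For the MDT group: "Patients who agreed to and accepted the recommendation of multidisciplinary assisted care mode were enrolled in the multidisciplinary assisted care model group". The next sentence says that these patients go on to further preventive intervention. For the other group: "Patients who did not agree to enter the multidisciplinary treatment mode were automatically entered into the routine treatment mode group".

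Between the two definitions, inside the MDT block, is a list of procedures and drug therapy. A patient who has any of them "shall be deemed to have received the standard medical treatment; otherwise, they were not". No time window is attached, and no outcome comparison by this label is described.

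The comparator is mentioned in two other places. Under the secondary objectives in Section 2: "The conventional diagnosis and treatment mode can match the patients not adopted in the same period". In Section 5, item 3 (sample size): "if compared with conventional diagnosis and treatment methods, patients matched with multiple factors in the same period are selected as the control group". That item expects 1,200 patients and does not split them by group.

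Section 7, item 1 lists CRF content under headings a) to h). Treatment is recorded as "Treatment medication; surgical conditions". No listed item is the MDT offer, the answer or its date. Study consent is a separate step that applies to every patient, as Section 9, item 2(2) states: "They will be selected after the subjects fully understood the trial, accepted the informed process, and signed the informed consent".

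**The concern.** Three things catch the eye.

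- **The definitions are not exact complements.** One uses two verbs (agreed and accepted), the other only one (did not agree). Taken literally, a patient who agrees and then does not accept has no group. The received/not-received label nearby could suggest that acceptance means later uptake of treatment.
- **The comparator is described in two ways.** Section 2 puts every decliner in the routine group automatically. The secondary objectives and Section 5 speak of matched patients from the same period. If those included patients who were never offered the MDT mode, they would have no answer date to start the clock.
- **The deciding date is not listed.** If group membership depended on a date that nobody recorded, a later analysis plan could not recover it.

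The stake would be immortal-time bias. If membership followed acceptance after enrolment, MDT patients would have to stay event-free until they accepted. Matching on baseline factors does not remove that advantage.

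**Working it through.** **Wording.** The definitions, in the order the text gives them, run: the patient agrees to and accepts the MDT mode; is enrolled in that group; then undergoes further intervention. The complement is not agreeing to enter. Both turn on one response to one offer, and treatment comes after assignment. No section describes an interval between agreeing and accepting, or moves a patient between groups according to treatment received. The English is plainly translated and doubles words elsewhere (the sample-size text in Section 5 repeats standardization), so two verbs for one act is the likelier explanation.

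**Comparator.** Section 2 defines who is in the routine group. The secondary objectives and Section 5 say that, if a comparison is made, controls are matched on several factors. Drawing matched controls from a defined group of decliners satisfies all three statements. A pool of never-offered patients is possible, but no section states one.

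**CRF.** Headings a) to h) are content categories and name no date for anything, including enrolment, surgery and adverse events. Headings a), b), c), f) and g) are open-ended. The missing MDT-answer date is therefore not evidence that it goes uncollected.

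**Size under a post-enrolment wait.** The protocol gives no event rate, wait or group split. Assume no true effect, event rate λ = 0.10 per year, τ = 1.5 years (Section 2 gives at least 1.5 years), an exponential wait with rate μ, time counted from enrolment, and patients with an event before acceptance in neither group.

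- Events: E = (1 − e^(−λτ)) − [λ/(λ+μ)]·(1 − e^(−(λ+μ)τ))
- Person-time: P = (1 − e^(−λτ))/λ − E[M·e^(−μM)], where M = min(event time, τ)
- Apparent rate ratio: (E/P)/λ

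For a mean wait of one month, μ = 12 per year. E = 0.1393 − 0.1/12.1 = 0.1310. P = 1.3929 − 0.1/12.1² = 1.3922. The ratio is 0.1310/(1.3922 × 0.10) = 0.94.

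| Share of MDT patients who wait | Mean 1 week | Mean 1 month | Mean 3 months |
|---|---|---|---|
| None (group fixed by the answer) | 1.00 | 1.00 | 1.00 |
| One quarter | 1.00 | 0.99 | 0.96 |
| One half | 0.99 | 0.97 | 0.92 |
| All | 0.99 | 0.94 | 0.83 |

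Rates of 5% or 15% per year change these ratios by at most 0.003.

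A harsher rule counts pre-acceptance events as routine. With 18-month risk r, a fixed lag of L months, a share q who would accept and h = −ln(1 − r)/18, the MDT risk is 1 − (1 − r)/e^(−hL). The routine risk is [(1 − q)r + q(1 − e^(−hL))]/[(1 − q) + q(1 − e^(−hL))]. For r = 0.10, L = 1 and q = 0.5 this gives 0.0947/0.1052 = 0.90. Over r of 10% and 20% and q of 30% to 70%, the risk ratio is 0.85 to 0.93 at one month and 0.62 to 0.80 at three months. At zero lag it is again 1.00.

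**Precision under either comparator.** Assume 20% of the 1,200 decline and an 18-month risk of 1 − e^(−0.15) = 0.139. Using all decliners compares 960 with 240; 1:1 matching compares 240 with 240. With SE(log RR) = √[(1 − 0.139)(1/e₁ + 1/e₂)], where e₁ and e₂ are the event counts:

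- 960 v 240: e = 133.7 and 33.4, SE = 0.179, 95% CI multiplier e^(1.96 × 0.179) = 1.42
- 240 v 240: e = 33.4 and 33.4, SE = 0.227, multiplier 1.56

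This is the usual loss of precision from matching. It is not a bias.

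**The case for a change.** The strongest case for a change concerns data capture. A registry is prospective, so the date of the MDT answer costs little to record at the time and is hard to reconstruct later. An analysis plan can define time zero but cannot use a date that was never collected. The protocol also does not say that matched controls come from the decliners, and a reader could form a never-offered pool. If MDT follow-up then started at acceptance and routine follow-up at enrolment, a hazard three times higher in the first three months would give apparent ratios of 0.98, 0.92 and 0.83 for mean waits of one week, one month and three months (by simulation; all inputs assumed). With a constant hazard the ratio is 1.00.

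Part of this stands: the source of the controls is not spelled out, and recording the answer date would be useful. But loss of the date is not established, because the CRF list is a summary with open headings and Section 9 keeps consent on file for every patient. The time origin, the matching method and any use of the received-treatment label are normally set in an analysis plan.

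The pre-lock review meant to "complete the final definition and judgment of the analysis population" (Section 7, item 2) is ordinary practice and says nothing about exclusions based on follow-up.

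**Conclusion.** No change to the plan follows. The group rule is one agree/decline answer at entry, and on that reading timing bias is nil (apparent ratio 1.00 under no effect). The ratios of 0.62 to 0.99 need a wait after enrolment, and for some of them a raised early hazard, that the protocol nowhere describes. They show what a different design would risk and do not measure an error in this one.

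What remains is a gap in wording. Sections 2 and 5 leave it to the reader to see that matched controls come from the decliners, and the CRF summary does not itemise the answer. A competent analyst would fix group by the answer, start both groups' follow-up there, and match within the decliners.

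The comparison is exploratory and secondary. Its main weakness, that patients choose their own group, would be the same however these sentences were worded. The conclusion rests on reading agreed and accepted as one act. It would change if the unseen flow chart or CRF showed that acceptance is a later, separate step.
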